## **Protocol Summary**

Protocol Number:	HP-00054854
Protocol Title:	Postoperative Heme Oxygenase Induction and Carbon Monoxide Production as a Novel Method to Assess Hepatic Regeneration and Predict Hepatic Related Morbidity After Partial Hepatectomy
Study Rationale:	The goal of this proposal is to elucidate the role of HO-1 induction in hepatic regeneration after partial hepatectomy (PH). There is a growing body of evidence that HO- 1 induction through CO production has an important role in cellular protection and regeneration. To test this concept, we will monitor endogenous CO production in patients who undergo PH and analyze the relationship between CO production and hepatic regeneration. Using this approach we will test the following two hypotheses: (1) HO-1 induction after PH is proportional to 
Study Objectives:	Specific Aim 1: To monitor the extent of HO-1 induction (by measuring endogenous CO production) in relationship to the extent of hepatic resection 1.1 Monitor CO in exhaled air of patients before liver resection, at 4 hours and 24 hours after PH 1.2 Monitor carboxyhemoglobin(COHb) in the arterial blood gas of patients before liver resection at 4 hours and 24 hours after PH 1.3 Analyze the relationship between CO production and the extent of hepatic resection assessed by computed scans liver volumetric study at one and three months after PH, size and weight of the resected specimen and operative report. Specific Aim 2: To analyze the relationship between HO-1 induction and the quality of post-hepatectomy liver regeneration after PH

	
 
2.1 Analyze the relationship between CO production and the quantity and quality of hepatic regeneration assessed by computed scans liver volumetric study at one and three months after PH and liver function tests after PH.
 
2.2 Determine the relation between postoperative liver related morbidity in patients undergoing PH and the extent of postoperative HO-1 induction
 

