
 
Assessment of postoperative liver function and regeneration:
 
Liver volumetry will be measured using image
 
J software downloaded from
 
http://rsbweb.nih.gov/ij/. The accuracy of this method was reported in a prior study.
 
Volumetric study will be performed based on CT scan studies obtained as standard of care preoperatively before each liver resection and at one and three months after each resection.
 
Collected data will be reported as percentage compared to the preoperative hepatic volume.
 
Specific Aim 2: To analyze the relationship between HO-1 induction and the quality of post-hepatectomy liver regeneration
 

 
2.1 Analyze the relationship between CO production and the quantity and quality of hepatic regeneration assessed by computed scans liver volumetric study at one and three months after PH and liver function tests.
 
2.2 Determine the relation between hepatic related morbidity in patients undergoing partial hepatectomy and their ability to induce HO-1
 

Study design: Aim 2.1: As CO is uniquely produced by HO reaction; its level was previously validated to check HO-1 induction. Checking this level and comparing outcome of the previously created three groups of patients (<25%, 25-50% and >50% PH) according to their ability to induce HO-1 after PH. Liver regeneration will be evaluated by radiological criteria at one and three months after PH as described above as well as laboratory criteria including liver function tests. Aim 2.2: HO-1 induction was found to offer beneficial protective effect in different clinical and surgical occasions. In this setting of PH, surgical complications in the perioperative (30 days) period graded by Clavien-Dindo Classification will be reported and analyzed regarding its relation with the ability to induce HO-1.
Procedures and Methods: Liver function tests routinely checked on daily basis till normalization will be monitored. This includes serum protein, Albumin, liver enzymes (AST and ALT), alkaline phosphatase and bilirubin level. The duration needed to this normalization will be checked as well as the trend of each of these laboratory parameters. Hepatic morbidity will be evaluated using the criteria used by the international study group of liver surgery being normalization of the INR and bilirubin by POD#5 while the severity

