#### Analyses:

All results will be collected in Excel Document. Analyses of groups based on the extent of liver resection and CO production. Results of different subgroups will be analyzed; comparison between groups will be performed by fisher test, paired and unpaired student t test, main Whitney test or ANOVA with repeated measurements when appropriate. Significance is defined as p<0.05.

Potential problems and alternative strategy: It is possible that HO-1 induction varies according to preoperative and intraoperative factors beside the patient own ability to induce HO-1. The most important known other factors are smoking and intraoperative blood transfusion will be reported in the study, however, other factors may exist and influence the result of this study. Preoperative factors may include preoperative use of chemotherapy and the presence of underlying liver cirrhosis. Intraoperative factors may include operative time and surgical technique (open or minimally invasive). In case of significance variance between patient s in the same group (same percentage of PH) Subgroup analysis including different variants (preoperative chemotherapy, perioperative

	blood transfusion and onen vorsus minimally
	blood transfusion and open versus minimally
	invasive technique) will be used to assess the
	effect of these factors.
Study Population:	125 participants enrolled locally; 125
	enrolled worldwide
Inclusion Criteria:	1-Patients plans to have partial liver
	resection for primary liver pathology or
	metastatic disease
	2-Patients able to comprehend and willing to
	sign the written consent form
Exclusion Criteria:	1-Patients with age less than 18 years
	2-Patients identified as part of the vulnerable
	populations as defined in the current
	application, except women with child bearing
	potential with negative pregnancy test
Study Treatment:	For Aim 1, after the patient's procedure, they
	will have to exhale into the device listed for
	collecting exhaled air specimen.
	For Aim 2, the patient's blood samples that
	are routinely collected after a hepatectomy
	will be used for analyzing serum protein,
	Albumin, AST and ALT, alkaline phosphatase,
	and bilirubin level.
	The duration of an individual's participation
	will be about 3 months +/- 2 weeks.
Study Procedures and Assessments:	Aim 1:
	Procedures and Methods
	- Protocol:
	For collecting exhaled air specimen, each
	patient will be instructed to exhale
	completely, and then

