	classification will be used to document
	surgical outcome of patients after PH.
Study Endpoints:	Aim 1:
	-CO output/production based on extent of
	liver resection, to be collected at 4 hrs and 24
	hrs after PH
	-CT scans looking at hepatic regeneration and
	one and three months after PH and liver
	function tests
Statistical Analyses:	Aim 1 Analyses:
	All results will be collected in Excel
	Document. Analyses of groups based on the
	extent of liver resection and CO production.
	Results of different subgroups will be
	analyzed; comparison between groups will be
	performed by fisher test, paired and
	unpaired student t test, main Whitney test or
	ANOVA with repeated measurements when appropriate. Significance is defined as
	p<0.05.
	ρ<0.05.
	Aim 2 Analyses:
	All results will be collected in Excel
	Document. Analyses of groups based on the
	extent of liver resection and CO production.
	Results of different subgroups will be
	analyzed; comparison between groups will be
	performed by fisher test, paired and
	unpaired student t test, main Whitney test or
	ANOVA with repeated measurements when
	appropriate. Significance is defined as
	p<0.05.
Study Duration:	15 years

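### Aim 2.2 plans no adjustment for extent of resection, so a pooled CO-morbidity comparison is biased against HO-1 protection if CO and morbidity both rise with extent

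*Combined protocol and SAP*

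**What the plan says.** The Protocol Summary states Aim 2.2 twice. Under Study Objectives the task is to "Determine the relation between postoperative liver related morbidity in patients undergoing PH and the extent of postoperative HO-1 induction". Under Study Design, 30-day complications are to be "graded by Clavien-Dindo Classification will be reported and analyzed regarding its relation with the ability to induce HO-1". The methods for Aim 2 add liver failure, graded A to C by the international liver surgery group's criteria. Neither statement names a test, a covariate or a stratification.

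The Analyses paragraph, which the Statistical Analyses entry repeats in the same words for Aims 1 and 2, offers "Analyses of groups based on the extent of liver resection and CO production" and says that "comparison between groups will be performed by fisher test, paired and unpaired student t test, main Whitney test or ANOVA with repeated measurements" will be used as appropriate. No regression model or stratified test is listed.

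Three extent groups (under 25%, 25-50%, over 50%) are created under Aim 1.3 and used again only in the Aim 2.1 text. Section 2 (Study Objective) gives two hypotheses: that induction is proportional to the extent of resection, and that failure to induce HO-1 appropriately goes with impaired regeneration. No formula or cut-off defines ability to induce or appropriate induction.

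**The concern.** Extent of resection is fixed at operation, before the 4-hour and 24-hour CO readings. If it drives both CO and morbidity, it is a confounder of their relation, not a step on the path from CO to outcome. The first link, from extent to CO, is the protocol's first hypothesis. The second, from extent to morbidity, is not stated in the documents and is assumed here.

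If both links hold, patients with high CO are disproportionately those with large resections and more complications. A pooled comparison then makes CO look less protective than it is, or harmful. The Aim 2.2 design text opens from the idea that HO-1 induction protects, so the bias runs against the effect that motivates the aim. The better hypothesis 1 holds, the less a pooled Aim 2.2 comparison can say about protection.

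The exposure is open as well. One statement of the aim uses the amount of induction. The other uses ability to induce, which could mean CO relative to what the resection would lead one to expect. The two readings lead to different analyses.

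**Working it through.** **Plan's own figure.** The plan gives 125 participants and alpha 0.05, with no power, effect size, event rate or dropout, so 125 cannot be reproduced. Event rates, extent effects and correlations below are assumptions, and tests are taken as two-sided.

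**Check 1: direction, by arithmetic.** Take three equal extent groups, with r0 the morbidity risk at low CO and h the share of patients with high CO. The true OR for high v low CO within every group is 0.5, so the high-CO risk is r1 = 0.5·r0/(1−r0) ÷ [1 + 0.5·r0/(1−r0)]. Pooled high-CO events are Σh·r1 and low-CO events Σ(1−h)·r0. Each CO level totals 1.5 in these units.

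- Moderate links: r0 = 0.15/0.25/0.35, h = 0.35/0.50/0.65, so r1 = 0.081/0.143/0.212. High-CO events 0.2377, low-CO events 0.345. Crude OR = (0.2377 × 1.155)/(1.2623 × 0.345) = **0.63**.
- Steep links: r0 = 0.10/0.25/0.45, h = 0.20/0.50/0.80, so r1 = 0.053/0.143/0.290. High-CO events 0.3142, low-CO events 0.295. Crude OR = (0.3142 × 1.205)/(1.1858 × 0.295) = **1.08**.
- No true effect (within-group OR 1.0): crude OR 1.24 (moderate) and 2.07 (steep).
- One link removed: with a flat 25% risk the crude OR is 0.50. With CO unrelated to extent it is 0.53, equal to the standardised OR.

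The standardised OR stays at 0.51-0.53 throughout, so the shift is confounding and not non-collapsibility. Both links are needed. In 2,000 simulated trials of 125 patients at within-group OR 0.5, a crude Fisher test finds protection in 15% (moderate) or 1% (steep). A Mantel-Haenszel test stratified on the three groups finds it in 31% or 26%.

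**Check 2: size, with continuous CO.** Assumed: extent uniform on 5-75% and standardised; CO = rho × extent + noise, with correlation rho = 0.3, 0.5 or 0.7; 12% liver failure (125 × 0.12 = 15 events). There were 2,000 trials per scenario at N = 125, and large-sample ORs came from N = 400,000. Triplets are for rho 0.3/0.5/0.7.

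| Extent OR per SD | Large-sample crude OR (true 0.70) | Crude Mann-Whitney significant, no CO effect (%) | Protection found, true OR 0.50: Mann-Whitney (%) | Same: Firth logistic, continuous extent (%) |
|---|---|---|---|---|
| 1.25 | 0.75-0.81 | 5.4/7.2/9.4 | 55/50/43 | 63/52/41 |
| 1.5 | 0.80-0.93 | 7.1/11.2/15.2 | 48/36/26 | 61/53/40 |
| 2 | 0.86-1.14 | 9.8/21.1/37.4 | 36/21/10 | 63/53/41 |
| 3 | 0.95-1.44 | 16.2/39.2/66.3 | 21/6/1 | 58/53/40 |

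Adjusted large-sample ORs (true 0.70) are 0.69-0.70 with continuous extent and 0.71-0.83 with three groups, so the groups leave some bias. With no CO effect, Firth regression on continuous extent rejects in 4.1-5.4% of trials.

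Separate Fisher tests in each extent group, with CO split at the group median and any of the three significant, find protection in only 11-22% at true OR 0.50. Running a listed test within groups is therefore a poor substitute for a model.

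For Clavien-Dindo grade (proportional odds, assumed grade shares 55/15/15/10/5%, true OR 0.70, extent OR 1.25-2), the crude OR is 0.74-1.14, three-group 0.70-0.78 and continuous 0.68-0.72.

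**The case against.** **The plan does not commit to a crude test.** A reader might infer that it does. The text does not say so: "Analyses of groups based on the extent of liver resection and CO production" can mean CO groups crossed with extent groups, Aim 2.1 compares the three extent groups by ability to induce, and the fallback paragraph speaks of variance among patients with the same percentage resected. That stands, and the gap is one of specification. But none of these passages settles Aim 2.2. The fallback is conditional and covers chemotherapy, transfusion and surgical technique; it does not adjust for extent.

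**Prediction does not need adjustment.** The title says "Predict Hepatic Related Morbidity After Partial Hepatectomy", and hypothesis 2 concerns regeneration, not morbidity. This stands too: the crude association is a valid answer to a predictive question. It does not answer the protection rationale that opens the Aim 2.2 design text.

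**Two listed tests would give different verdicts on the same data.** A reader might infer this from the open list. The documents do not support it. The only ANOVA listed is with repeated measurements, so a two-factor ANOVA of CO on outcome and extent group is not a listed test. Even with no confounding at all, Mann-Whitney and such an ANOVA differ in 12-30% of simulated trials at true OR 0.50, so disagreement between them is not a measure of this bias.

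**False findings would nearly all point to harm.** This fails when confounding is weak. At extent OR 1.25 and correlation 0.3, with no CO effect, about 4% of trials are falsely significant for harm and about 1% for protection.

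**The sizes are assumed.** True. The large effects need an extent OR of 2-3 per SD, and extent was linear on the log-odds scale in every run of Check 2, which favours the continuous term.

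**Conclusion.** The concern holds as a gap in specification. Aim 2.2 has no extent-adjusted analysis, and the tests listed are unadjusted unless run within extent groups. A pooled comparison is biased against HO-1 protection on two conditions: CO rises with extent (hypothesis 1, which the study is still to test) and extent raises morbidity (an assumption, with no rates in the documents). If either fails, extent does not confound the relation.

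The direction is established; the size is not. Under the assumed inputs the bias is modest up to an extent OR of 1.5 per SD, and enough to hide or reverse protection at 2-3. Adjustment does not rescue a weak signal: at true OR 0.70 the crude test finds protection in 0-17% of trials and Firth regression in 13-24%. The point should be fixed because the remedy is cheap, not because the study is shown to fail.

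**What to change.** For Aim 2.2, prespecify a model of morbidity on CO induction with extent of resection as a covariate. Use percent resected or future liver remnant percent, preferably as a continuous term. Use Firth logistic regression for liver failure and proportional odds for Clavien-Dindo grade. Define ability to induce HO-1 in the same sentence. Base any statement about protection on the extent-adjusted estimate, and report the crude association beside it as the predictive result.

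State that residual confounding remains. The protocol itself says that induction may vary with "preoperative and intraoperative factors beside the patient own ability to induce HO-1", and it names smoking, transfusion, chemotherapy and cirrhosis. As an illustration, assume 25% transfused, more often in larger resections, CO raised by 0.5 SD and a morbidity OR of 2.5. With true OR 0.70 and extent OR 1.5-3, the crude OR is 0.92-1.70, extent-adjusted 0.78-0.85, and adjusted for extent and transfusion 0.69-0.71.

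**Cost.** Analysis wording only: remnant volume, segments resected and specimen weight are already collected under Aim 1.3. Intervals widen. The standard error of the CO coefficient grows by roughly 1/√(1−rho²), which is 1.05 at correlation 0.3 and 1.40 at 0.7; simulation gave 1.05-1.12 and 1.38-1.43. If extent does not affect morbidity, adjustment costs power at true OR 0.50: 66% to 63% at correlation 0.3, and 64% to 39% at 0.7. At extent OR 1.25 and correlation 0.7 the loss is small (43% to 41%). From extent OR 1.5 upward the adjusted test had more power in every scenario run.

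### Liver tests are followed only until they normalize, so comparing their trend as daily levels among patients still tested, or by complete-series ANOVA, attenuates the level difference from about POD5

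*Combined protocol and SAP*

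**What the plan says.** Under Aim 2, Procedures and Methods, the Protocol Summary states: "Liver function tests routinely checked on daily basis till normalization will be monitored". The tests are listed: "This includes serum protein, Albumin, liver enzymes (AST and ALT), alkaline phosphatase and bilirubin level". Two outcomes are taken from them: "The duration needed to this normalization will be checked as well as the trend of each of these laboratory parameters". The same text recurs under Study Procedures and Assessments.

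These results serve Aim 2.1, where regeneration is judged radiologically "as well as laboratory criteria including liver function tests". The comparison is described as "comparing outcome of the previously created three groups of patients (<25%, 25-50% and >50% PH) according to their ability to induce HO-1".

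Besides Fisher's test, the Analyses text names "paired and unpaired student t test, main Whitney test or ANOVA with repeated measurements when appropriate", and adds: "Significance is defined as p<0.05". The Statistical Analyses row repeats this for both aims.

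The document does not define trend, fix a common window of days, say whether draws stop test by test or only when all tests are normal, or say how days after normalization are handled. Sections 3 and 4 make clear that the results come from routine care with no interference in treatment, so the study does not control when draws end.

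**The concern.** Observation ends because the outcome has been reached. On a later postoperative day, the patients with a result are those who have not yet recovered. A t or Mann-Whitney test on that day's values compares the slow tail of the better-recovering group with most of the poorer-recovering group. Repeated-measures ANOVA in its standard form needs complete series, so over a week it keeps mainly slow recoverers from both groups.

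At stake is one of the two laboratory outcomes of Aim 2.1. If stronger HO-1 induction does go with faster recovery, a trend analysis done in either of these ways could show a much smaller difference, or none, because of who is left to measure.

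**Working it through.** **Nothing to reproduce.** The plan gives no effect size, SD or derivation for its 125 participants. The sizes below come from simulation, and every marker parameter is an assumption.

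**Inputs from the plan.** Daily draws to normalization; trend as an outcome; the listed tests; p<0.05 (taken as two-sided); 125 participants. Two equal groups are assumed: 125/2 = 62.5, so 62 per group.

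**Model A (assumed).** ALT-type marker, peak 300 on POD1, upper limit 45, log-linear decline with no floor. Between-patient SD 0.45 (log peak) and 0.25 (log half-life); noise SD 0.12. Half-lives 2.0 v 2.6 days. Sampling stops at the first value at or below 45.

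Typical time from peak to limit = half-life × log2(300/45) = half-life × 2.74, which is 5.5 v 7.1 days.

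True log difference on a given day = days since peak × ln 2 × (1/2.0 − 1/2.6) × exp(0.25²/2) = days × 0.0825.
- POD5: 4 × 0.0825 = 0.33
- POD7: 6 × 0.0825 = 0.50
- POD9: 8 × 0.0825 = 0.66

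The simulated full-data values agree (0.32, 0.49 and 0.65). Among patients still tested:
- POD5: 0.27 against 0.32, a loss of 1 − 0.27/0.32 = 16%. A second run gave 0.28 against 0.34 (18%), with power falling from 88% to 79%.
- POD7: 0.23 against 0.49, a loss of 53%. Power fell from 98–99% to 59–65% over three runs. By then 42% of fast and 18% of slow recoverers had left the series.
- Half-lives 2.0 v 2.4, POD7: 0.17 against 0.36, a loss of 53%; power 83% to 38%.

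The POD9 figure should not be used. Without a floor, the true difference comes largely from values below the normal limit. With an assumed floor of 25, the full-data difference is 0.38 at POD7 and 0.29 at POD9.

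**Model B (assumed).** log(value/upper limit), start 1.2 (SD 0.35), slope SD 0.08, residual SD 0.15, floor −0.5, draws on days 1–10, 20,000 patients per group. Cells show full data → still tested; losses use unrounded differences.

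| Slopes, good/poor | Sampled day 7, good/poor | Day 3 | Day 5 | Day 7 | Day 10 |
|---|---|---|---|---|---|
| −0.30/−0.15 | 28%/78% | 0.30→0.30 | 0.57→0.46 (−20%) | 0.63→0.43 (−32%) | 0.48→0.35 |
| −0.30/−0.20 | 28%/63% | 0.20→0.20 | 0.37→0.29 (−22%) | 0.38→0.26 (−32%) | 0.23→0.23 |
| −0.25/−0.10 | 46%/89% | 0.30→0.29 | 0.58→0.50 (−15%) | 0.76→0.52 (−31%) | 0.75→0.49 |
| −0.40/−0.20 | 7%/64% | 0.40→0.39 | 0.67→0.52 (−22%) | 0.54→0.44 (−18%) | 0.27→0.34 |

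With 62 per group and slopes −0.30/−0.20, power went from 99% to 93% on day 5 and from over 99% to 58% on day 7.

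**Complete series, days 1–7 (Model B, same row order).** Average level difference: 0.39→0.12, 0.25→0.05, 0.42→0.18, 0.43→0.07. Difference in change from day 1 to day 7: 0.63→0.61, 0.38→0.40, 0.76→0.67, 0.53→0.72, so it errs either way.

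**Methods that use each series up to its stop (Model B).**

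| True slope difference | Per-patient slope | Mixed model |
|---|---|---|
| 0.150 | 0.154 | 0.155 |
| 0.100 | 0.104 | 0.096 |
| 0.150 | 0.154 | 0.141 |
| 0.200 | 0.199 | 0.200 |

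In Model A the mixed model on the truncated data gave 0.49, against 0.50 on full data (30 runs).

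**Carrying the last value forward (Model A).** POD7 0.29 against 0.49; POD9 0.18 against 0.65. At POD7 it restores most of the power (94% against 65% among those still tested) but not the size of the difference.

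**The case against.** A reader might infer that any comparison of recovery is understated and that the whole laboratory part of Aim 2.1 is pulled toward no relation. The documents do not support that, for four reasons.

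- Trend is undefined and the tests apply when appropriate. A per-patient slope up to normalization, compared by the listed unpaired t test, is compatible with the text. In Model A it had about 100% power (2.0 v 2.6 days) and 97% (2.0 v 2.4).
- Duration to normalization stands in the same sentence, measures fast against slow recovery directly, and is not distorted by this stopping rule. Mann-Whitney on the day of normalization had 97% and 77% power in the same two scenarios. The separate POD5 criterion for INR and bilirubin does not rest on daily means either.
- POD5 is the only postoperative day the protocol names, and the loss there is modest.
- If draws continue until all tests are normal, tests that normalize early stay observed and the loss shrinks.

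All of this stands and limits the point. It does not remove it: trend is a separately planned outcome, repeated-measures ANOVA is the only longitudinal method named, and nothing in the text steers the analyst away from the two analyses that fail. Even if draws run until all tests are normal, patients still leave on recovery.

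**Conclusion.** The point holds for two ways of analysing trend that the plan leaves open: daily levels among patients still tested, and complete-series repeated-measures ANOVA. For daily levels the difference is essentially intact at POD3, loses about 15–22% at POD5 and about 18–53% at POD7; complete-series averages lose more. The direction on days 5 and 7 was the same in every scenario run. Beyond that, and for complete-series change scores, the error can go either way.

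The sizes rest on assumed courses for a marker that falls to normal, on test-by-test stopping, and on two equal groups. Protein and albumin, which would rise to normal, were not modelled. The mixed-model result relies on stopping being driven by the observed values and on a roughly log-linear course up to normalization.

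The wording should be changed before analysis. It is not a flaw in the data collection or in the duration outcome.

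**What to change.** In the Aim 2 analysis text:

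1. Analyse the trend of each test with a linear mixed model on log values of all observed results, with random intercept and slope and a CO-by-day term, over an early window of days fixed in advance.
2. State that daily means and complete-series ANOVA will not be compared among patients still being tested.
3. For any single-day display, keep normalized patients in as normal: show the proportion normalized, or use a rank test that ranks them best. Do not use a carried-forward value to estimate the size of the difference.
4. Record whether routine draws end test by test or when all tests are normal.

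The cost is one mixed model per test (six as listed) and reliance on an approximately log-linear course within the window, which should be checked against plotted profiles. Patient care and data collection do not change.
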